12.2.4. SVR evaluations

SVR evaluations will be assessed on the majority of participants at week 24 (12 weeks after treatment completion). For a minority of participants who receive 24 weeks of treatment, the SVR evaluations will take place at week 36. The window for the SVR assessment visit will be -2 weeks (10 weeks after treatment completion) to 60 weeks after treatment completion (i.e., study weeks 22-72). Visits outside this window are allowed with documentation of reason for early/late visit.

If a participant misses the visit window, every attempt should be made to contact participant and complete the SVR evaluation and other evaluations through the end of the study follow-up period.

At this visit, the following assessments will be done in all arms

- Scan biometric to confirm identity
- Administer a brief survey on substance use, risk behavior and quality of life
- Update medication history
- Provide updated contact/locator information
- EHR review, clinical exam, and vital signs
- Draw blood for HCV RNA testing
- Abstract HIV RNA information from government ART book (if HIV infected)
- Pregnancy test (if female)
- Schedule next appointment

The post-SVR evaluations will be scheduled in relation to when participants complete the SVR evaluations.

While COVID-19 safety precautions are in place, in order to reduce face-to-face contact, we will administer surveys, update medication history and collect locator information over the phone. Participants will have to come to the ICC for a brief exam and blood draw (and pregnancy test as needed). Exceptions will be made for this in-person requirement in cases where 1) COVID-19 precautions make travel to the site challenging; and 2) participants are in rehabilitation facilities or cannot travel to the site for another reason.

In cases where the HCV RNA ≥30 IU/ml and <1000 IU/ml, a repeat sample will be drawn ≥14 days after the initial sample as long as it is within the SVR window (i.e., up to 60 weeks after treatment completion)

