If a CD4 within 90 days prior to screening is not available in the EHR, a CD4 count will be obtained from an approved local laboratory (HIV-positive participants).

12.3.9.9. Virologic studies.

HCV RNA testing

Screening HCV RNA and SVR HCV RNA testing will be conducted at the YRGCARE Infectious Disease Laboratory in Chennai, India, which is a DAIDS-certified laboratory.

Samples for HCV RNA testing will be processed and shipped as described in Section 12.3.9.11.

Any sample with HCV RNA between 30 – 1000 IU/ml will require resampling for confirmation in a second sample drawn ≥14 days after the initial sample.

HIV RNA testing

HIV RNA testing is generally done at government ART centers. Available HIV RNA results will be abstracted from the ICC EHR.

HCV Core Antigen testing.

For post-SVR visits, re-infection will be assessed using the Abbott ARCHITECT HCV Ag assay. This testing will be conducted at the YRGCARE Infectious Disease Laboratory in Chennai, India.

Samples for HCV Core Antigen testing will be processed and shipped as described in **Section 12.3.9.11**.

12.3.9.10. Stored plasma/serum. Stored plasma and serum will be collected at the indicated visits for future HCV/HIV studies and shipped to the central YRGCARE Infectious Disease Laboratory.

Stored specimens may be used for HCV genotyping/sequencing needed to differentiate between relapse and reinfection among participants failing to achieve SVR. We will also test for the presence of resistance-associated substitutions (RASs) in these specimens by sequencing the nonstructural protein 5A (NS5A) and nonstructural protein 5B (NS5B) regions.

12.3.9.11. Specimen preparation, handling and shipping. All staff handling laboratory specimens will undergo training in Good Clinical Laboratory Practices (GCLP). Additional training certification and recertification will be provided by the Central YRGCARE team in India. The YRGCARE lab is a DAIDS certified laboratory. Certification of the personnel and the procedures on specimen collection, preparation, handling, storage and shipping will be required before sites start collecting and shipping specimens.

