STATISTICAL ANALYSIS PLAN

A precision randomized trial to evaluate the impact of tailored hepatitis C virus (HCV) treatment adherence support on HCV treatment outcomes in HIV/HCV co-infected and HCV mono-infected people who inject drugs (PWID) in India

NCT04652804

Supporting Treatment Outcomes among PWID (The STOP-C Study)	
	-
	Funded by:
	onal Institute of Allergy nfectious Diseases
R01-Al-145555-01 Industry Support Provided by:	
Protocol Chair/Co-Chair:	[name] MPH, Co-Chair [name] [name] MPH, Co- Chair
DAIDS-ES Document Number:	DAIDS-ES ID 38666
Version Number:	1.0
Version Day Month Year:	5 January 2024

SIGNATURE PAGE

I agree to conduct the analysis in accordance with the relevant, current protocol.

I agree to personally conduct or supervise the analysis.

Co-Principal Investigator: [name] MPH / Professor

Signed:

Date: 1/5/24

Co-Principal Investigator: [name], PHD MPH / Professor

Signed: Date: 1/5/24

1. Primary outcome

The primary outcome is sustained virologic response (SVR) defined as HCV RNA < lower limit of quantification (LLOQ) 10 – 60 weeks after completion of treatment (cure). The primary analysis will be intention to treat and will be stratified by the risk of treatment failure (minimal and elevated).

The primary analysis will compare the proportion achieving SVR across level of support (low, medium, high intensity) within the two strata of risk (minimal and elevated) independently. Using log-binomial models (or their extensions, i.e., Poisson regression with robust variance estimation) including adjustment for site as a fixed effect, in the elevated risk stratum, we will compare the proportion achieving SVR in those who received the low and moderate intensity interventions (in separate models) to those who received the high intensity intervention resulting in a relative risk (RR). Analysis will be repeated for the minimal risk stratum except comparing those who receive the high and moderate intensity interventions to the low intensity intervention.

Primary comparisons will be intention to treat. That is, the study population for this analysis will include everyone who was randomized. Individuals with missing data on the outcome of interest either due to loss-to-follow-up or death will be treated as failures.

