- **1d. Subgroup analyses**. Subgroup analyses will explore whether the effect of the intervention in either risk stratum varies by the prognostic score itself as well as by other covariates of interest including age, employment status, HIV status and treatment, drug use, injection drug use, alcohol use, homelessness, depressive symptoms, medication for opioid use disorder (MOUD), distance to study site, readiness for HCV treatment and study site. Interactions will be included in regression models that also adjust for site.
- **1e. Exploratory analyses**. Using viral sequence analysis of baseline and SVR samples, we will reclassify persons with evidence of reinfection (vs. treatment failure) as having achieved SVR. The primary outcome and sensitivity analyses by arm within strata described above will be repeated after this reclassification. We will also conduct exploratory analyses to explore correlates of HCV treatment failure and reinfection overall and by HIV status.

2. Secondary outcomes

Secondary outcomes are 1) treatment completion defined as completing the prescribed course of treatment (12/24 weeks); 2) adherence; 3) reinfection defined as testing positive for HCV Core Ag after achieving SVR; and 4) HIV viral suppression defined as HIV RNA<LLOQ.

2a. Treatment completion.

Those who discontinue treatment prior to the end of their prescribed course will be considered as failures for this analysis. In the elevated risk stratum, using log binomial regression models (or their extensions, i.e., Poisson regression with robust variance estimation), including adjustment for site as a fixed effect, the proportion completing treatment in those who received the low and moderate intensity interventions will be compared to those who received the high intensity intervention (in separate models) resulting in a relative risk (RR). For those at minimal risk of failure, analyses will be similar except comparing the high and medium intensity interventions to the low intensity interventions.

2a.1.Sensitivity analyses.

- Regression models will be repeated considering site as a random effect (instead of as a fixed effect).¹
- Regression models will be repeated without adjustment for site.
- To account for covariates that are differentially distributed by arm or prognostic for the outcome:

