Annual assessments of HIV viral load among HIV/HCV coinfected participants in the 7 ICCs are expected as part of other ICC activities and standard of care at Indian government ART centers. All available viral load measurements for HIV/HCV co-infected PWID enrolled in the trial will be used. Viral suppression will be defined as HIV RNA less than LLOQ. We will compare viral suppression across two groups defined by primary outcome status, which will be cured vs. not cured using logistic regression with generalized estimating equations (GEE) to account for repeated measures within individuals. Because these groups will be defined by the primary outcome and no longer balanced by randomization, analysis will be adjusted for confounding factors including demographics, substance use, needle sharing, MOUD, SSP use, social support and frequency of visits to the ICC. Analyses will be combined across all groups but we will include a covariate for the classification of risk of treatment failure (minimal or elevated) and intervention received. In order to account for missing data due to loss-to-follow-up, we will use inverse-weighting methods.^{4,5}

2d.1. Sensitivity analyses. We will vary the threshold for HIV viral suppression (<150 copies/ml vs. 400 copies/ml vs. 1000 copies/ml) and will also incorporate the revised definition of SVR vs. treatment failure using sequence data.

3. Exploratory analysis

3a. Impact of interventions on medication for opioid use disorder (MOUD) utilization. Daily MOUD utilization data is available in the electronic health record. We will explore the impact of the interventions within strata by arm on new MOUD initiation and MOUD retention using methods of survival analysis, logistic regression with GEE and growth mixture models. Analyses will be adjusted for site. Additional sensitivity analyses will be similar to those reported in the primary and secondary outcome analyses and will include accounting for the prognostic score.

3b. Impact of interventions on quality of life.

Quality of life data is captured at the SVR visit and at semi-annual post-treatment follow-up visits. Using logistic and linear regression with GEE, we will explore the impact of interventions within strata on quality of life after treatment.

3c. Impact of interventions on mortality.

Using Poisson regression, we will explore the impact of interventions within strata on all-cause mortality.

3d. Effect of delays in treatment completion on SVR.

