Additional exploratory analyses will evaluate the impact of non-adherence and delays in completing treatment on SVR. Initial analyses will incorporate data from all three arms. Two variables will be calculated: 1) the percentage of doses completed (as described above); and 2) days to treatment completion. While the scheduled course of treatment will be 84 days for most, participants will be instructed to take all of the doses prescribed (even if doses are missed and the total time for treatment completion extends beyond 84 days). In separate models, log-binomial models (or their extensions, i.e., Poisson regression with robust variance estimation) will be used to estimate the association between 1) estimated adherence and SVR; and 2) days to treatment completion and SVR. These analyses will be combined across risk strata and treatment arm but these variables will be included as covariates. Additional analysis will be conducted exclusively among participants assigned to Arm 3 (high intensity support) where weekly adherence data will be collected using biometric data.

3e. Estimation of heterogeneity in treatment effect and estimation of average treatment effect.

Additional analyses will be completed to estimate heterogeneity in treatment effect and the average treatment effect for the primary (SVR) and secondary outcomes defined above.

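### SAP 3d relates adherence and treatment delay to plain SVR, without the reinfection reclassification planned in 1e, 2c.1 and 2d.1

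*SAP*

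**What the plan says.** SAP section 1 and Protocol 15.2.1 define SVR by viral load alone: HCV RNA below the quantification limit, 10 to 60 weeks after the end of treatment. Nothing in the definition separates relapse from a new infection.

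SAP 1e deals with this by sequencing baseline and SVR samples: "we will reclassify persons with evidence of reinfection (vs. treatment failure) as having achieved SVR". It then sets the scope: "The primary outcome and sensitivity analyses by arm within strata described above will be repeated after this reclassification". SAP 2c.1 repeats the reinfection analysis with a sequence-based outcome, and the HIV suppression sensitivity analyses in 2d.1 "will also incorporate the revised definition of SVR vs. treatment failure using sequence data".

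SAP 3d has no such provision. It announces: "Additional exploratory analyses will evaluate the impact of non-adherence and delays in completing treatment on SVR". Separate models relate SVR to the percentage of doses completed and to days to completion. On adjustment it says: "These analyses will be combined across risk strata and treatment arm but these variables will be included as covariates". No other covariate is named.

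On specimens, Protocol 12.3.9.10 is permissive: "Stored specimens may be used for HCV genotyping/sequencing needed to differentiate between relapse and reinfection among participants failing to achieve SVR". Protocol 18.3.3 makes storage optional for the participant.

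**The concern.** Missed or late doses can plausibly lead to relapse or non-response. They cannot cause a new infection after cure. An analysis of what missed or late doses do to cure should therefore not count reinfection among its failures without at least showing the result with reinfection set apart.

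The exposure in 3d is observed, not assigned. If continued injecting makes a participant both less adherent and more likely to be reinfected, some of the reinfections will appear as an apparent cost of poor adherence. In 2d the SAP recognizes that groups formed after randomization are not balanced, and adjusts for substance use, needle sharing, MOUD, SSP use and visit frequency. Section 3d has neither that adjustment nor the reclassified outcome. At stake is how the trial's statement on missed or late doses will be read.

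**Working it through.** The plan gives no sample size, expected effect or reinfection rate for 3d, so it has no figure to reproduce. The visit window does reproduce: for a 12-week course, 12 + 10 = 22 and 12 + 60 = 72, the study weeks in Protocol 12.2.4. The scheduled visit at week 24 is 24 − 12 = 12 weeks after completion.

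**Step 1: where the reclassified outcome is used.**

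| Analysis | Sequence-based outcome planned? |
|---|---|
| SVR by arm within strata, with its sensitivity analyses (1e) | Yes |
| Reinfection (2c.1) | Yes |
| HIV suppression (2d.1) | Yes |
| Adherence and delay against SVR (3d) | No |

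**Step 2: is a shared cause supported by the text?** The preliminary adherence model in Protocol 15.5, built on early ART adherence, includes injection frequency and OAT use. The reinfection factors in SAP 2c include ongoing substance use, needle sharing and MOUD (the SAP's term for OAT). Protocol 12.3.10 collects risk factors for both outcomes in one questionnaire. The overlap is in the documents; its strength is not.

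**Step 3: illustration of size.** All rates are assumptions. True cure is set at 95% in both groups, so the true RR is 1.00. With reinfection rate r per person-year and t = weeks from completion to test / 52:

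observed SVR = 0.95 × exp(−r t)

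spurious RR (less adherent / adherent) = exp(−(r1 t1 − r0 t0))

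Both groups tested at the scheduled 12 weeks, t = 12/52 = 0.231:

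| Rates per 100 PY, adherent vs less adherent | Calculation | RR |
|---|---|---|
| 2 vs 6 | exp(−0.04 × 0.231) | 0.991 |
| 5 vs 15 | exp(−0.10 × 0.231) | 0.977 |
| 10 vs 20 | exp(−0.10 × 0.231) | 0.977 |
| 5 vs 5 | exp(0) | 1.000 |

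Wider assumed gaps move it further at the same visit: 5 vs 20 gives 0.966 and 10 vs 30 gives 0.955.

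**Step 4: effect of test timing.** If both groups were tested at 60 weeks (t = 1.154), 5 vs 10 would give exp(−0.05 × 1.154) = 0.944, against 0.989 at 12 weeks. If adherent participants were tested at 12 weeks and less adherent ones at 36 weeks (t = 0.692), 5 vs 15 would give exp(−(0.15 × 0.692 − 0.05 × 0.231)) = 0.912. Over the first three rate pairs in the table, that timing split gives 0.891-0.964, and a 12 against 60 week split gives 0.812-0.937. Equal rates of 5 with later testing alone give 0.977 at 36 weeks and 0.955 at 60.

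**Step 5: after the change.** With complete and accurate reclassification the illustration returns 0.95/0.95 = 1.00.

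This is a crude two-group contrast. It does not include the stratum adjustment, does not use percentage of doses as a continuous exposure, and does not model days to completion.

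**The case against.** The other side has several good points. Section 3d is exploratory, serves no listed hypothesis, and cannot change a primary or secondary result. It adjusts for risk stratum, and the preliminary score behind the stratum includes injection frequency and OAT use. SAP 1e also plans to explore correlates of treatment failure and of reinfection, and adherence is an obvious candidate. These points limit the importance of the gap but do not close it. A two-level stratum leaves variation within each level, as SAP 3e itself says of the score. The correlates sentence names neither adherence nor delay and leaves the 3d outcome as it is.

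Three stronger readings are tempting, and the documents do not support them.

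- A reader might infer a spurious RR of 0.81-0.96. Those values need less adherent participants to be tested at 36 or 60 weeks and adherent ones at 12. The visit is scheduled at the same point for everyone on the same course length, and no passage says who attends late. Setting such values beside the RRs in Protocol Table 15.4.1 is also not like for like, because those are minimal detectable differences between arms.
- A reader might infer that the arm comparisons are immune because arms are randomized. Reinfection and visit timing arise after randomization and can differ by arm. SAP 2c asks whether the intervention affects reinfection, and 1e repeats the by-arm analysis.
- A reader might infer that the reclassified outcome must replace SVR as the main outcome in 3d. That is a preference. Sequencing is permissive and storage optional, so the reclassified outcome may be incomplete.

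**Conclusion.** The gap is real: 3d counts reinfection before the SVR test as failure, and the SAP's own reclassification does not reach it. Because the exposure is not randomized and predictors of non-adherence overlap with reinfection factors, the association can be biased away from the null, towards harm from missed or late doses. The stratum covariate removes only part of this.

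The size cannot be derived from the documents. Under assumed rates of 2-10 against 6-20 per 100 person-years, with everyone tested at the scheduled 12 weeks, the unadjusted spurious RR is about 0.98-0.99. For those rates it grows only if tests, especially among less adherent participants, fall much later in the window. With equal rates and equal timing there is no bias. The consequence is confined to an exploratory analysis; primary and secondary conclusions are unchanged.

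**What to change.** Add 3d to the analyses that are repeated with the sequence-reclassified outcome of SAP 1e, with reinfection counted as cured and relapse or non-response as failure. Report this beside the result for unreclassified SVR. Give the number of viremic participants who could not be sequenced, and show the 3d results with them classified once as treatment failures and once as reinfections.

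The cost is a sentence or two in the SAP and a rerun of two models on sequence data already planned. The small downside is incomplete classification, because specimen storage is optional; showing both classifications makes the extent of that visible.

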11.2.1. Regimens

For participants without HIV infection and who are HIV-infected but not on an efavirenz containing regimen, the treatment will be once-daily generic oral fixed-dose combination of sofosbuvir/ velpatasvir (SOF/VEL) containing 400 mg of SOF and 100mg of VEL. Treatment duration will be 12 weeks taken orally with or without food. If a participant is co-infected with HIV and on an efavirenz containing regimen they will have the option to switch to a non-EFV containing regimen (e.g., DTG) for at least two weeks prior to initiation of DAA therapy with SOF/VEL. The government of India is modifying their guidelines and a combination of tenofovir/emtricitabine/dolutegravir TDF/FTC/DTG will be the preferred first-line regimen. The government is expected to roll-out this combination in December 2019 ahead of the initiation of this trial.

If the participant is unable to modify the ART regimen to a non-EFV containing regimen, they will receive once-daily generic oral fixed-dose combination of sofosbuvir/daclatasvir (SOF/DAC) including 400 mg of SOF and 60 mg of DAC (an additional 30 mg pill of DAC will be dispensed as

required). Treatment duration for this group will be guided by the presence/absence of compensated cirrhosis and genotype. For those with genotype 3 infection and compensated cirrhosis, treatment duration will be 24 weeks. For all others, treatment duration will be 12 weeks. All treatment will be oral with or without food.

For Arms 1 and 2, the Study Nurse will observe the first dose being taken by the participant upon completion of all entry evaluations. Participants will receive only one bottle of study product at a time.

Participants in Arms 1 and 2 will be scheduled to have a scheduled pick-up/drop off for the next bottle of study medication three days prior to when their last pill is due from that bottle. Participants will be asked to retain empty study bottles and return them to the study staff.

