^{*}For participants who receive 24 weeks of therapy, the SVR visit will take place at 36 weeks

^{**}For participants who receive 24 weeks of therapy, these visits will take place at weeks 60, 84, 108, 132, 156, 180, 204, 228

^{***}Additional doses will be observed for Arm 3 (36 to 84 for those receiving 12 weeks of treatment and 72 to 168 for those receiving 24 weeks)

^{****}Only assessed on participants who achieve HCV cure

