12.2.3. On treatment evaluations

Participants in all arms will have brief on-treatment evaluations at 4, 8 and 12 (end of treatment) weeks after the entry visit (treatment start).

A minority of participants will receive 24 weeks of treatment and so will have additional ontreatment evaluations at 16, 20 and 24 (end of treatment) weeks.

Because some of these visits include medication pickup, the goal is to conduct the visits within a +/- 2 day window. However, up to a +5 / -14 day window will be permissible for visits with medication pick up (visits outside this window are allowed if approved by study doctor).

The following assessments will be done

- Scan biometric to confirm identity
- Administer a brief survey on substance use, risk behavior and medication adherence, record answers in eCRF
- Update medication history
- Provide updated contact/locator information
- Count the pills remaining in the prior bottle
- Provide the next bottle of medication (Arms 1 and 2 only; at all except 12 week visit)
- Observe that day's dose if it has not been taken
- Draw blood for repository (Week 12 [or Week 24] visit only)
- Pregnancy test (if female and pregnancy suspected)
- Assess adverse events
- Schedule next appointment

While COVID-19 safety precautions are in place, we will attempt to complete these visits with minimal face-to-face contact and so will offer alternatives. For the on-treatment evaluations, we will complete surveys, updating of locator information and counseling over the phone. We will offer multiple options for medication refills other than pickup at the ICC including drop off to home or some other mutually agreed upon location. Prior bottles will be collected and stored for several days before pills are counted. For the end of treatment visit, surveys will be completed over the phone but an in-person visit will be preferred for the blood draw. Exceptions will be made for this in-person requirement in cases where 1) COVID-19 precautions make travel to the site challenging; and 2) participants are in rehabilitation facilities (e.g., drug detoxification programs) or cannot travel to the site for another reason.

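### SAP 3d measures delay in raw days to completion, mixing 84-day and 168-day prescribed courses, and does not say how participants without an SVR result enter

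*SAP*

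**What the plan says.** SAP 3d asks how non-adherence and late completion relate to SVR. It specifies the exposures as "Two variables will be calculated: 1) the percentage of doses completed (as described above); and 2) days to treatment completion". It notes "While the scheduled course of treatment will be 84 days for most", and adds that participants are told to finish all doses even if that takes longer. Each exposure goes into its own log-binomial or robust Poisson model. On pooling and adjustment it says: "These analyses will be combined across risk strata and treatment arm but these variables will be included as covariates". Protocol 15.7.2.3 describes the same variables, pooling and covariates.

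The other course length comes from Protocol 11.2.1. For participants with HIV who cannot leave efavirenz and so receive SOF/DAC, it says: "For those with genotype 3 infection and compensated cirrhosis, treatment duration will be 24 weeks". Protocol 12.2.3 confirms "A minority of participants will receive 24 weeks of treatment" but gives no number.

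Section 3d names no analysis set, no rule for a missing SVR result, and no value of days for people who never complete. SAP section 1 has a rule, "Individuals with missing data on the outcome of interest either due to loss-to-follow-up or death will be treated as failures", but states it in the paragraph that opens "Primary comparisons will be intention to treat". SAP 1a defines a set limited to completers with an SVR visit, and SAP 1b plans censoring weights and multiple imputation. Section 3d chooses none of these.

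**The concern.** The purpose of 3d is to show how much missed or late dosing matters for cure. Total days to completion measures lateness only when everyone is prescribed the same number of days, and here they are not. The listed covariates do not repair this: arm is randomized, and the preliminary score factors in Protocol 15.5 do not include regimen, genotype or cirrhosis. The 24-week group is also clinically distinct, so any difference in its SVR would be attributed to time taken.

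The second exposure has a separate gap. SAP 2b includes refill and pill-count measures, so a participant who drops out has a low dose percentage and may also have no SVR result. How that missing result is coded can then decide whether an association appears.

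**Working it through.** **1. Course lengths.** 12 × 7 = 84 days, which reproduces the SAP's figure, and 24 × 7 = 168 days. The upper ends of the observed-dose ranges in the footnote to Protocol Table 12.1 agree: "36 to 84 for those receiving 12 weeks of treatment and 72 to 168 for those receiving 24 weeks". The gap between two punctual courses is 168 − 84 = 84 days.

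**2. Leverage of the 24-week courses.** Let f be the share prescribed 24 weeks and s the SD of true delay, taken as unrelated to prescribed duration. Neither value is in the documents, so both are assumed. The share of raw-day variance due to prescribed duration is f(1−f)84² / [s² + f(1−f)84²], with 84² = 7056.

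| f | s (days) | f(1−f) × 7056 | Share of variance |
|---|---|---|---|
| 0.1% | 10 | 7.0 | 7.0/107.0 = 7% |
| 0.5% | 10 | 35.1 | 35.1/135.1 = 26% |
| 1% | 10 | 69.9 | 69.9/169.9 = 41% |
| 2% | 10 | 138.3 | 138.3/238.3 = 58% |
| 1% | 20 | 69.9 | 69.9/469.9 = 15% |

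**3. Direction when duration is unrelated to SVR.** Variance share is not bias, so this was simulated: 200 runs of Poisson regression with 2,600 completers each, and SVR of 95% on time falling by 0.3% per day of delay. Delay was gamma with shape 0.5 and scale 20, so the mean is 0.5 × 20 = 10 days and the SD is 20 × √0.5 = 14.1 days. The mean RR per 14 days was:

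| f | Days beyond prescribed course | Raw days |
|---|---|---|
| 0 | 0.958 | 0.958 |
| 0.5% | 0.959 | 0.965 |
| 1% | 0.958 | 0.969 |
| 2% | 0.958 | 0.976 |
| 5% | 0.958 | 0.985 |

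A hand check at 1%: the slope shrinks by 200/(200 + 69.9) = 0.74, and exp(−0.003 × 14 × 0.74) = 0.969. Raw days pull the estimate toward 1, while days beyond the prescribed course leave it in place.

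**4. Untested participants in the dose-percentage model, if missing were scored as failure.** Assume 95% SVR among tested participants at every adherence level, so the true RR is 1.00. Let m be the untested share. Then RR (low vs high adherence) = 0.95(1 − m_low) / [0.95(1 − m_high)].

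- m_low = 25%, m_high = 8%: 0.75/0.92 = 0.82
- m_low = 40%, m_high = 8%: 0.60/0.92 = 0.65
- m_low = 10%, m_high = 5%: 0.90/0.95 = 0.95
- m_low = m_high = 5%: 1.00

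The artefact appears only when untested shares differ by adherence. Among tested participants the RR in this illustration is 1.00 by construction.

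**The case against.** The strongest reply is that the affected group may be almost empty. A 24-week course requires HIV co-infection, an efavirenz regimen that cannot be changed, genotype 3 and compensated cirrhosis, and Protocol 11.2.1 expects a dolutegravir-based first-line regimen to be rolled out before the trial starts. That stands as a limit on size. At a 0.1% share the contribution to variance is small, and it shrinks further if delays are widely spread. It does not make raw days the right scale.

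Four stronger readings are tempting, and the documents do not support them.

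- A reader might infer that 3d enters untested participants as SVR failures. It does not say so. The rule in SAP section 1 is tied to the primary comparisons, and the SAP contains other ways of handling a missing SVR.
- A reader might infer that the SAP defines delay as days beyond 84. It states no such rule. The 84-day offset follows from entering unscaled days in an analysis presented as one of delay.
- A reader might infer that scoring missing as failure also builds an association into the days model. Non-completers have no completion date, and among completers this would require late finishers to be untested more often, which nothing in the documents shows.
- A reader might infer that the 24-week courses would manufacture a delay effect. With duration unrelated to SVR the result is dilution. A shift in another direction needs SVR to differ in that group, and the documents give no figure for that.

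The dose percentage is already relative to the course, so the raw-days problem does not touch that model.

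**Conclusion.** The point holds for the days variable as written: 3d mixes prescribed duration with lateness, and nothing elsewhere in the protocol or SAP corrects this. How much it matters cannot be fixed from the documents. Over the assumed shares of 0.1% to 2% with a delay SD of 10 days, prescribed duration makes up about 7% to 58% of exposure variance. The estimate is diluted toward 1 if duration is unrelated to SVR, and could move either way if SVR differs in the 24-week group.

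On untested participants, the finding is an omission and not a coding error. A false adherence association arises only if missing is scored as failure in the dose-percentage model and low adherers are untested more often; the RR of 0.82-0.65 rests on the assumed shares of 25-40% versus 8%. The analysis is exploratory, so the consequence is confined to what 3d reports about missed and late dosing.

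**What to change.** In SAP 3d, define delay as days from first dose to completion minus the prescribed 84 or 168 days, counted so that a punctual course scores zero, and fit this model among completers. Restricting to 12-week courses is an acceptable alternative, and it also removes any difference in SVR between the two duration groups. Say explicitly that participants who never complete are outside the days model.

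For the dose-percentage model, name the analysis set as participants with an HCV RNA result inside the SVR window. Apply inverse probability of censoring weights of the kind SAP 1b plans for the primary outcome, and report missing scored as failure as a sensitivity analysis.

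This takes a few sentences and needs no new data. The cost is a smaller analysis set and reliance on the weights, which correct for loss only so far as the weighting model captures its causes.
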